### **3.3 Study Schema**

#### ***Priming Treatment Schema***

**Figure 1:** Schematic diagram of study events. All patients will receive a fixed dose of pembrolizumab at 200 mg i.v. every three weeks. The lung SBRT will be administered at week 3 on Monday, Wednesday and Friday. The first cohort will be dosed at 30 Gy in 3# and the second cohort will be dosed at 54 Gy in 3#.

### **3.4 Follow-Up after stopping Pembrolizumab**

#### **3.4.1 30 Day Safety Follow-Up Visit**

All patients will be required to attend a safety follow-up visit 30 days after the last dose of pembrolizumab or before the initiation of a new anti-cancer treatment, whichever comes first. All adverse events (AEs) and serious adverse events (SAEs) that occur prior to the safety follow-up visit should be reported as described in section 7. After the safety follow-up any unresolved AEs at the patient's last visit should be followed up for as long as medically indicated, but without further recording in the CRF.

#### **3.4.2 Follow-Up for Discontinued Pembrolizumab without Disease Progression**

Patients who discontinue pembrolizumab for any reason other than disease progression will move into the follow-up phase and should be assessed every 9 weeks ( $63 \pm 7$  days) and by radiologic imaging as per standard of care to monitor disease status. Every effort should be made to collect information regarding disease status until the start of new anti-cancer therapy, disease progression, death, withdrawal or end of the study. Information regarding post-study anti-cancer treatment will be collected if new treatment is initiated.

#### **3.4.3 Survival Status Follow-Up Phase**

Once a patient experiences confirmed disease progression or starts a new anti-cancer therapy, the patient moves into the survival follow-up phase and will be followed up every 12 weeks to determine their disease status. This will be done by reviewing their medical notes and / or contacting the patient or GP directly. Patients will remain on this follow-up until death, withdrawal of consent, or the end of the study, whichever occurs first.

### **3.5 Study Termination**

The 'end-of-trial' is defined as the date when the last patient has completed the 'off-study' visit or the final follow-up visit, whichever is happens last.

#### **3.5.1 Criteria for Early Trial Termination**

Early trial termination will be the result of the criteria specified below:

1. Quality or quantity of data recording is inaccurate or incomplete
2. Poor adherence to protocol and regulatory requirements

3. Incidence or severity of adverse drug reaction in this or other studies indicates a potential health hazard to patients
4. Plans to modify or discontinue the development of the study drug
5. If DLT is seen at dose level 1 in 2 out of 3 or 2 out of 6 patients

In accordance with the conditions of supply agreement with MSD, ample notification will be provided to the sponsor (via RM-CTU) and sites should alterations to the drug supply change. This is to allow time for appropriate adjustments to be made in regards to the patient's treatment.

### **3.6 Treatment after End of Study**

Following participation in the study patient care will be decided by the local doctor according to standard practice.

## 4 SELECTION OF PATIENTS

---

### 4.1 Screening and Enrolment

The Investigator at site will keep a record of all patients screened for entry into this study. Copies of the screening logs will be filed in the Site File. For each patient, the primary reason for exclusion will be recorded. Diagnostic data obtained as part of the patient's standard care will be used to determine eligibility provided they fall within the protocol defined timelines. Written informed consent must be obtained prior to the patient undergoing any study specific procedures.

### 4.2 Registration

When the patient signs the consent form they will be allocated a trial ID that will be used to identify the patient for all future assessments.

Patients can be registered and allocated a trial ID number by contacting the RM-CTU on:

[contact]

[contact]

Email: [[contact]](mailto:[contact])

Between Monday to Friday, 9 am to 4 pm.

Once all the screening assessments have been completed and the data entered on the CRFs the patient will be assessed for eligibility. If eligible the patient will begin on the trial. If the patient is not eligible then the local investigator will make alternative arrangements for the treatment of the patient. The trial ID will be a unique number that once assigned will become the permanent study identifier for that patient. In the event a patient is registered onto the study but does not begin treatment, then that patient's trial ID will not be reassigned. Treatment will begin within 7 days from the date eligibility has been confirmed. To ensure patient confidentiality patients will only be identified on CRFs, other trial specific forms and all communication to RM-CTU using their assigned trial ID. It is the CI's responsibility to maintain a confidential record of the identity i.e. full name, date of birth and hospital number for the patients enrolled in this study and their assigned trial ID. At the end of the study this record should be archived along with the Site File.

### 4.3 Patient Replacement Strategy

Additional patients may be enrolled in a given cohort to ensure that the required number of evaluable patients in each cohort is achieved. A patient that discontinues the trial for progressive disease within 3 months of the last dose of radiotherapy will not be evaluable for DLTs and therefore will need to be replaced. A patient that discontinues the trial for a drug-related AE will not be replaced and will be counted in the evaluable population of patients for the respective cohort. However, patients found to have active

pneumonitis on C1D1 of pembrolizumab or day 1 of radiotherapy will be removed from the trial and can be replaced. Also patients who do not reach follow-up 3 months post completion of lung SBRT for reasons other than progression or toxicity can be replaced by new patients in that cohort to ensure there is a minimum of 3 (or 6 if required) patients in each cohort.

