In the dose escalation phase, a minimum of 3 patients will be required per dose level being assessed. A minimum gap of 1 week will be left between the treatment of the first and the second, and between the second and the third patients with the combination of pembrolizumab and lung SBRT to mitigate against multiple patients suffering from acute toxicity. The DLT period for this study is 12 weeks from the last dose of lung SBRT (i.e. at C6D1). The dose escalation will be considered by the Safety Review Committee (SRC) once the 3rd or 6th patient in the cohort has completed the DLT period. If no DLT is observed at a dose level,

then lung SBRT will be dose escalated to the next dosing level (see Table 1). If 1 out of 3 patients experience a DLT, then the cohort will be expanded to 6 patients. If 1 in 6 patients experience a DLT, then the dose will be escalated to the next dosing level. However, if  $\geq 2$  in 6 patients experience a DLT then the maximum administered dose (MAD) will have been reached, and the RP2D will be the previous dosing level that will be used for the dose expansion cohorts. If the MAD is seen at dose level 1 then the study will be terminated. While waiting for 3 or 6 patients to complete the DLT period, no additional patients will be recruited. Further patients can only be recruited after the SRC has reviewed the toxicity data for the cohort and taken a decision to dose escalate to the next cohort or expand the current cohort to 6 patients.

Once the MTD has been determined the trial enters the dose expansion phase (unless the MTD is dose level 1). Here, 12 patients will be treated with the RP2D of SBRT combined with pembrolizumab.

If there is ongoing clinical benefit at 24 months, the CI/PI will need to discuss with the sponsor and MSD, on a case by case basis for the continuation of pembrolizumab.

**Table 1:** Lung SBRT dose levels and pembrolizumab dosing during the dose escalation and dose expansion phase.

Dose Level	Pembrolizumab Dose	Lung SBRT to part of a lung lesion
1	200 mg i.v. over 30 minutes, every 3 weeks	30 Gy in 3# (Monday, Wednesday, Friday)
2	200 mg i.v. over 30 minutes, every 3 weeks	54 Gy in 3# (Monday, Wednesday, Friday)
Dose expansion	200 mg i.v. over 30 minutes, every 3 weeks	RP2D

SBRT: Stereotactic Ablative Body Radiotherapy; Gy: Gray; i.v.: intravenous; mg: milligrams;  
RP2D: Recommended Phase 2 Dose; #: fraction.

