## **Non-Haematologic:**

Any NCI CTCAE  $\geq 3$  grade non-haematological toxicity that is definitely, probably or possibly related to the combination of pembrolizumab and lung SBRT including the following:

[figure not shown]
- Increased MRC dyspnoea score  $> 2$  grades from baseline and/or acute dyspnoea grade  $\geq 4$  (or CTCAE dyspnoea grade  $\geq 3$ ) persisting for  $> 7$  days (including weekend).
- Pneumonitis/pulmonary infiltrates grade  $\geq 3$  persisting for  $> 7$  days (including weekend).
- Oesophagitis grade  $\geq 3$  persisting for  $> 7$  days (including weekend).
- Toxicity leading to interruption of radiotherapy for  $> 7$  days (including weekend).

Escalation to the next dose level will not proceed until the following criteria are satisfied by the SRC:

- If 0 out of 3 patients experience a DLT, escalation to the next dose level can proceed.
- If 1 out of 3 patients experiences a DLT, a further 3 patients will be recruited at that dose level.
  - If 1 out of 6 patients experiences a DLT, then escalation to the next dose level can proceed.
  - If  $\geq 2$  out of 6 patients experience a DLT, the MAD will have been reached. The RP2D will be the dose level prior to when the DLTs were observed or dose level 2 if no DLTs were observed.  
All patients in the expansion cohort will have lung SBRT dosed at the RP2D (see Figure 1).
- If 2/3 patients experience a DLT then the MAD will have been reached and the expansion cohort phase will begin at the previous dose level unless this occurs at dose level 1.
- If dose level 1 is not tolerated due to DLTs, the expansion cohort will not go ahead and the trial will be terminated.

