### **5.3.11.3 Confirmation of Disease Response**

Per RECIST v1.1 & irRC (Appendix 6 & 7), response should be confirmed by a repeat radiographic assessment no less than 4 weeks from the date the response was first documented. The scan for confirmation of response may be performed at the earliest 4 weeks after the first indication of response, or at the next scheduled scan, whichever is clinically indicated.

Immunotherapeutic agents may produce anti-tumour effects by potentiating endogenous cancer-specific immune responses. The response patterns seen with such an approach may extend beyond the typical time course of responses seen with cytotoxic agents and can manifest a clinical response after an initial increase in tumour burden or even the appearance of new lesions. Therefore standard RECIST v1.1 may not provide an accurate response assessment of immunotherapeutic agents such as pembrolizumab.

Therefore, RECIST v1.1 will be used with the following adaptations:

- If radiologic imaging shows initial progressive disease (PD), tumour assessment should be repeated  $\geq 4$  weeks later in order to confirm PD with the option of continuing treatment while awaiting radiologic confirmation of progression.
  - Patients may continue treatment while waiting for confirmation of PD if they are clinically stable as defined by the following criteria:
    - Absence of signs and symptoms indicating disease progression
    - No decline in ECOG performance status
    - Absence of rapid progression of disease
    - Absence of progressive tumour at critical anatomical sites requiring urgent alternative medical intervention. When feasible, patients should not be discontinued until progression is confirmed. This allowance to continue treatment despite initial radiologic progression takes into account the observation that some patients can have a transient tumour flare in the first few months after the start of immunotherapy, but with subsequent disease response. Patients that are deemed clinically unstable are not required to have repeat imaging for confirmation of progressive disease.

- If repeat imaging shows a reduction in the tumour burden compared to the initial scan demonstrating PD, treatment may be continued /resumed.
- If repeat imaging confirms progressive disease, patients will be discontinued from study therapy.

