Hypophysitis	2-4	Toxicity resolves to Grade 0-1. Therapy with pembrolizumab can be continued while endocrine replacement therapy is instituted	Toxicity does not resolve within 12 weeks of last dose or inability to reduce corticosteroid to 10 mg or less of prednisone or equivalent per day within 12 weeks.
Hyperthyroidism	3	Toxicity resolves to Grade 0-1	Toxicity does not resolve within 12 weeks of last dose or inability to reduce corticosteroid to 10 mg or less of prednisone or equivalent per day within 12 weeks.
	4	Permanently discontinue	Permanently discontinue
Hypothyroidism		Therapy with pembrolizumab can be continued while thyroid replacement therapy is instituted	Therapy with pembrolizumab can be continued while thyroid replacement therapy is instituted.
Infusion Reaction	3-4	Permanently discontinue	Permanently discontinue
Pneumonitis	2	Toxicity resolves to Grade 0-1. If recurrent Grade 2 pneumonitis occurs pembrolizumab should be permanently discontinued.	Toxicity does not resolve within 12 weeks of last dose or inability to reduce corticosteroid to 10 mg or less of prednisone or equivalent per day within 12 weeks.
	3-4	Permanently discontinue	Permanently discontinue
Renal Failure or Nephritis	2	Toxicity resolves to Grade 0-1	Toxicity does not resolve within 12 weeks of last dose or inability to reduce corticosteroid to 10 mg or less of prednisone or equivalent per day within 12 weeks.
	3-4	Permanently discontinue	Permanently discontinue
All Other Drug-Related Toxicity 	3 or Severe	Toxicity resolves to Grade 0-1	Toxicity does not resolve within 12 weeks of last dose or inability to reduce corticosteroid to 10 mg or less of prednisone or equivalent per day within 12 weeks.
	4	Permanently discontinue	Permanently discontinue

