#### 8.1.1 Primary Endpoint

For the primary endpoint of establishing the MTD and RP2D of lung SBRT that can be safely combined with pembrolizumab, the toxicity rate will be stated as the proportion of patients who have had a DLT calculated along with an exact binomial 95% confidence interval. All toxicities will be tabulated by type, grade and dose level.

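### Read literally, section 4.3 drops a DLT already seen when the patient later leaves for progression, and the maxima of 12 and 24 leave no room for the replacements that 4.3 requires

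*Combined protocol and SAP*

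**What the plan says.** Three rules in section 4.3 matter here.

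- Progression: "A patient that discontinues the trial for progressive disease within 3 months of the last dose of radiotherapy will not be evaluable for DLTs", and such a patient has to be replaced.
- Drug toxicity: "A patient that discontinues the trial for a drug-related AE will not be replaced and will be counted in the evaluable population of patients".
- Remaining cases: patients who miss the three-month follow-up "for reasons other than progression or toxicity can be replaced by new patients in that cohort".

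The section also allows extra enrolment into a cohort until its evaluable number is reached. It sets no ceiling.

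The decision rules refer to patients, not to evaluable patients. Section 3.2: "If 1 out of 3 patients experience a DLT, then the cohort will be expanded to 6 patients". Section 3.2.1: "If 2/3 patients experience a DLT then the MAD will have been reached"; it also escalates after 1 DLT in 6 and declares the MAD at 2 or more in 6. Section 8.1.1: "the toxicity rate will be stated as the proportion of patients who have had a DLT", with no denominator defined. Section 8.1 adds only that patients with incomplete safety observation are evaluated separately.

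On numbers, the Trial Summary limits recruitment to 12 in escalation and 24 overall, and section 3.1 repeats 24 recruited. Section 3.2 caps patients allocated in Part A at 12 and patients treated in the study at 24. Section 8.2 builds these from two cohorts of 3 to 6 plus 12 in expansion. None of these places mentions replacements.

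**The concern.** Two sets of stated rules do not fit together.

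First, take a patient who has a DLT, stays on trial, and then leaves for progression inside the window. Under 4.3 this patient is not evaluable. Under 3.2, 3.2.1 and 8.1.1 the DLT counts. The count that drives escalation, and hence the MTD and RP2D, is then not uniquely defined.

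Second, 4.3 makes replacement of progressors mandatory and unlimited, while the maxima are set at the bare cohort sizes. A team following 4.3 could exceed the limits in 3.2. Respecting those limits could mean deciding on fewer evaluable patients than the 3+3 rule needs.

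**Working it through.** **1. The plan's own figures.** 2 × 3 = 6, 2 × 6 = 12 and 12 + 12 = 24. The stated numbers reproduce exactly, with zero replacements.

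**2. When the DLT gap can arise.** A DLT that makes the patient leave falls under the drug-related AE rule and is counted. Table 8 (section 6.2.9.2) permanently stops pembrolizumab for several grade 3–4 toxicities, pneumonitis among them. It only holds the drug for others, such as grade 3 events in the row "All Other Drug-Related Toxicity". A related grade 3 non-haematological toxicity is a DLT under 3.2.1, so a patient can have a DLT and remain on trial.

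**3. Timing.** Twelve weeks after C1D19 is day 19 + 84 = 103. Section 3.2 equates this with C6D1 (day 106), and 4.3 says 3 months (about day 110). Section 5.3.11.2 puts the first CT at week 9 (day 63). Table 3, whose column headings are not fully legible in the text available, appears to put it at C5D1 (day 85). Section 5.3.11.3 says: "When feasible, patients should not be discontinued until progression is confirmed", and confirmation takes at least 28 days.

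- From a day-63 CT, the earliest confirmed exit is day 63 + 28 = 91, inside the window.
- From a day-85 CT, it is day 113, or day 106 if the CT is 7 days early. That is at or beyond the end of the window.

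Clinically unstable patients need no confirmation and can leave sooner. The documents therefore do not fix how often the case occurs.

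**4. Effect on a decision.** Suppose the patient is excluded and the replacement has no DLT.

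| DLT counted | DLT excluded | Change |
|---|---|---|
| 1/3: expand | 0/3 | escalate |
| 2/3: MAD | 1/3 | expand |
| 2/6: MAD | 1/6 | escalate |

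**5. Illustrative replacement fraction f.** The plan gives none. Assume exponential PFS with the medians cited in section 1.1.4.2 (3.0 to 4.0 months), no SBRT effect, exit at a day-63 CT without confirmation, and every PFS event treated as a progression exit. Then f = 1 − 2^(−t/median), with 30.44 days per month.

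- Counted from the last SBRT fraction, t = 63 − 19 = 44 days: f = 0.222 (4.0 months) to 0.284 (3.0 months).
- Counted from C1D1, t = 63 days: f = 0.301 to 0.380.
- f = 0.10 is an arbitrary lower value to represent exits delayed by confirmation.

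**6. Chance that Part A exceeds 12 treated, given n evaluable needed.** This is P(Binomial(12, 1 − f) < n).

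| f | n = 6 | n = 9 | n = 12 |
|---|---|---|---|
| 0.10 | 0.0001 | 0.026 | 0.718 |
| 0.222 | 0.007 | 0.267 | 0.951 |
| 0.284 | 0.029 | 0.458 | 0.982 |
| 0.380 | 0.125 | 0.730 | 0.997 |

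**7. How many evaluable patients are needed.** Worked example with assumed DLT rates of 10% at level 1 and 20% at level 2.

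- Level 1: P(0/3) = 0.9³ = 0.729; P(1/3) = 3 × 0.1 × 0.9² = 0.243; P(1/3, then 0/3) = 0.243 × 0.729 = 0.177; P(2 or 3 of 3) = 0.028.
- Level 2: P(expand) = 3 × 0.2 × 0.8² = 0.384; P(close at 3) = 0.616.
- n = 3: 0.028.
- n = 6: 0.729 × 0.616 + 0.243 × 0.271 = 0.515.
- n = 9: 0.729 × 0.384 + 0.177 × 0.616 = 0.389.
- n = 12: 0.177 × 0.384 = 0.068.

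Overrun at f = 0.10: 0.515 × 0.0001 + 0.389 × 0.026 + 0.068 × 0.718 = 0.059. At f = 0.222: 0.515 × 0.007 + 0.389 × 0.267 + 0.068 × 0.951 = 0.172.

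Repeating this for level 1/level 2 rates of 5/10, 10/10, 10/20, 10/30, 20/20, 20/30 and 30/30% gives these ranges:

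- f = 0.10: 3–7%.
- f = 0.222–0.284: 11–28%.
- f = 0.301–0.380: 21–44%.

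Across these scenarios 12 evaluable patients are needed in only 3–9% of paths.

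**The case against.** The strongest reply to the first part is that the conflict is small and already guarded. Exits for drug-related AEs are counted, and 4.3 does not allow replacement for toxicity under its last rule. The committee reviews a cohort's toxicity before more patients enter (3.2, 3.2.1, 10.9), and 3.5.1 allows termination for toxicity. All of that stands. A reader might infer that toxicity is hidden or that 4.3 understates the DLT rate. The documents support neither: the event is on record, and if progression is independent of DLT, excluding all progression exits leaves the rate unbiased on average. What remains is that the literal rule for progression contradicts the counting rules, and nothing in the text reconciles them.

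On the second part, 4.3 itself authorises extra patients, and the word required in 8.2 can be read as evaluable. That helps 8.2. It does not help 3.2, which caps patients allocated and treated, or 3.1 and the Trial Summary, which cap recruitment.

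The overrun probabilities are open to fair criticism. The higher ones rest on exit at a week-9 CT without confirmation, against the preference in 5.3.11.3 and possibly against Table 3. They also count deaths as progression exits. A reader might take from step 6 that overrun is close to certain. That holds only where both levels expand, at the higher replacement fractions.

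**Conclusion.** Both parts hold as conflicts between stated rules and figures, and should be fixed.

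The DLT gap is narrow and its frequency cannot be estimated from the documents. It matters because one patient can change a decision made on 3 to 6 patients. The case for change is that an observed DLT should not drop out of that count, not that the written rule has been shown to be biased.

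The maxima contain no allowance for mandatory replacements, so following 4.3 can breach them. The documents give no replacement rate and are unclear about the first CT. The chance of Part A passing 12 is therefore illustrative: about 3–7% at an assumed 10% replacement, and 11–44% at 22–38%. These figures rest on the assumed DLT rates, exponential PFS and, for the upper range, unconfirmed exit at week 9. Whether 4.3 reaches Part B is unstated, but this is minor because DLT evaluability drives escalation only.

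**What to change.** In section 4.3, state that a patient with a DLT in the window is always evaluable and counted, whatever the later reason for leaving, and that only DLT-free patients with incomplete follow-up are replaced.

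In the Trial Summary and sections 3.1, 3.2 and 8.2, restate 12 as the maximum number of DLT-evaluable patients in Part A. Give 24 either as exclusive of replacements or with an explicit replacement allowance. The first-CT timing in section 5.3.11.2 and Table 3 should be reconciled before an allowance is chosen.

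The cost is a few sentences and a larger stated patient number. There is also a statistical cost, to be noted in 8.1.1: DLT-free progressors are still replaced while every DLT counts, so the DLT rate becomes conservative. With p the true rate, and progression exit independent of DLT, the apparent rate is p / (p + (1 − p)(1 − f)). For p = 0.20 and f = 0.10 it is 0.20 / (0.20 + 0.80 × 0.90) = 0.217. At f = 0.222–0.284 it is 0.24–0.26, and at f = 0.380 it is 0.29.
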